#### Study Procedures / Outcome Measures.

Patient Characteristics Related to Pain and Music: This battery of questionnaires is intended to understand key aspects of pain, mood, and function as quickly and efficiently as possible.

 Demographics: Sex, age, race/ethnicity, marital status, education level, and body mass index (BMI) will be assessed in the context of standardized case report forms. Sex is an important biologic variable to investigate as centralized pain is more common in females, and is probably largely responsible for the fact that nearly any chronic pain condition is 1.5 – 2 times more common in women than in men.

- Medication List: A list of the medications participants are taking for pain and medications that may impact heart rate or pain sensitivity (i.e. opioid or analgesic medications).
- Fibromyalgia-ness (FMness): FMness is a measure of pain and co-morbid symptom extensiveness and severity. It is calculated by combining the scores from the Widespread Pain Index with the Symptom Severity Scale from the 2011 FM Survey to derive a continuous metric purportedly indicative of the degree of CNS pain amplification present in a given individual.
- Fibromyalgia Functional Status: We will assess the current health and functional status in FM patients using the Revised Fibromyalgia Impact Questionnaire (FIQ-R). The FIQ-R measures physical functioning, work status, and overall well-being.
- Clinical Pain Severity: Pain severity and functional interference due to pain will be assessed using the Brief Pain Inventory (BPI). The BPI is validated for chronic, non-malignant forms of pain, and asks patients to rate their current pain intensity, as well as their worst, least and average pain in the 7 days (0-10 NRS) and has been recommended by IMMPACT as a measure of choice for the assessment of pain in clinical research.
- Depression and Anxiety: To avoid patient burden with the multiple domains, this study will take advantage of the static short forms developed by the NIH roadmap initiative PROMIS. The PROMIS short forms will be used for Depression and Anxiety.
- Catastrophizing: Catastrophizing is associated with worse pain and the progression of chronic pain will be 6-item catastrophizing scale from the Coping Strategies Questionnaire(CSQ-CAT).
- Music Experience: Participants will also rate their music listening habits (i.e. frequency, styles, reasons for listening, etc.) using the Brief Music Experience Questionnaire (MEQ). The Brief MEQ is a 53 item self-report measure of music centrality in the respondent's life, his or her musical aptitude, and experience with and reaction to music. Participants will also be asked to rate their familiarity with the music or sounds and how much they liked the music or sounds after each testing session.
- Impulsivity: Using the 27-item Kirby Delay Discounting Task, a type of impulsivity can be measured by determining the value participants see in rewards if they are offered at different time points (eg. \$25 now OR \$60 in 21 days).

Quantitative Sensory Testing (QST): Pain testing will be performed using the Multimodal Automated Sensory Testing (MAST) System, a computerized QST device developed at the University of Michigan, and currently being employed in several clinical trials, including the NIH MAPP Network.

- Mechanical Pain Sensitivity (MPS). MPS will be assessed by applying discrete pressure stimuli to the thumbnail bed. The MAST system will deliver an ascending series of 5-s duration stimuli at 25-s intervals, beginning at 0.50 kg/cm2 and increasing in 0.50 kg/cm2 intervals up to tolerance or a maximum of 10 kg/cm2. Pain intensity will be rated after each stimulus on a 0 (no pain) 100 (extreme pain) numerical rating scale (NRS). Pressure pain threshold and tolerance will be determined from this procedure, as well as the PAIN50, the pressure intensity that provokes a response halfway between threshold and tolerance.
- Temporal Summation (TS). TS is the perceived increase in pain intensity to repeated stimulation at a constant stimulus intensity and is believed to reflect central sensitization. A 256 mN pinprick stimulus (MRC Systems, Heidelberg, Germany) will be applied once to the forearm or hand, followed by a train of 10 identical stimuli (1 Hz). Following the single stimulus and the train of 10 stimuli, patients will report the pain intensity of the pinprick sensation using a 0-100 NRS. This procedure will be repeated 3x. The mean pain rating of the three stimulus trains will be divided by the mean pain rating of the single stimuli to calculate a wind-up ratio (*WUR*); a WUR >1 indicates temporal summation.

Music and sound delivery: Auditory stimuli will be presented using an iPod and Bluetooth noise-cancelling headphones. Listening will begin 10 minutes prior to QST and will continue for the duration of the QST, for a total of 1 hour and 10 minutes. The listening condition will be a single bout on one of two days of testing. This is a two-arm parallel design RCT with Testing as usual (no-sound) and placebo control (nature sounds).

Heart Monitoring: Subject's electrocardiogram (ECG) will be recorded with a measurement device (Biopac/AcqKnowledge software) that consists of a computer-operated recording device and amplifier. The recording device and amplifier are attached to standard snap-on ECG electrodes. Three ECG electrodes are placed: one under the collar bone, one under the rib cage on the opposite side, and a ground on the abdomen. ECG will be recorded throughout each testing session. The time of each condition (passive listening vs. active listening with sensory/pain stimulus) will be recorded by the investigator. The ECG will be uploaded to Kubios software for analysis. Metrics of heart rate and variability in time-, frequency, and non-linear domains will be compared between conditions (passive vs. active listening) and between sounds (nature sounds vs. music).

Music characteristics: The musical selections will be professional recordings of instrumental Classical music selected by the researcher (See Appendix 1). All participants will hear the same pieces in the same order. Instrumentation ranges from piano solo to full orchestra, but they are without lyrics or heavy percussion. Pitch ranges across the pieces, but is standard across participants and not controlled by either the participant or the researcher. Tempo for all of the pieces is slow (~60 beats per minute). The pieces are in either major keys or minor keys, but all consist primarily of consonant harmonies and sustained melodic phrases. Participants will control the volume to their individual comfort level.

Placebo control: Professional recordings of nature sounds selected by the researcher without added music will be used as the active placebo control condition. All participants will hear the same recording. This active control condition will allow for non-musical analgesic effects, such as distraction, to be controlled in the experimental design. Participants will control the volume to their individual comfort level.

Mitigation of bias: We propose to use several strategies to mitigate potential bias in this study. Participants will be randomized to experimental or placebo group, group allocation will be concealed from personnel and they will be blinded throughout testing and analysis. Patients cannot be blinded as they will know whether they are hearing nothing, music, or nature sounds during testing. Our counterbalancing of testing days will help to ensure that attrition is not affecting one condition to a greater degree than another. Finally, our strategy to avoid potential publication bias is that by having both a no-sound control and a placebo nature sound control, we will be able to determine whether a) there is an analgesic effect of distraction in this population, and b) whether that effect is greater for music over another distracting auditory stimulus.

Study Limitations and Plans to Overcome Them: Recruitment: We do not anticipate that there will be any difficulty with participant recruitment. Given the clinically significant volume of fibromyalgia patients seen at the [name], Comprehensive Spine Center, we are confident that subject enrollment will be achievable within the allotted timeframe. Also, we plan on using the innovative recruitment programs available at KUMC to assist investigators with participant recruitment including the Frontiers Registry and the Pioneers Community

Research Recruitment Registry. Our project budget includes a financial incentive for patient participation which will aid in recruitment and compliance with study procedures.

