#### II. SPECIFIC AIMS

Aim 1: Determine whether music listening during pain sensitivity testing has an analgesic effect on pain thresholds and tolerance and whether this effect is of greater magnitude in comparison to a non-musical auditory stimulus in patients with Fibromyalgia (FM). In order to accomplish this

Aim, patients with FM will undergo a variety of quantitative sensory testing (QST) procedures in order to KUMC – HRPP- 03/12/2015 Page 1 of 19 fully characterize their peripheral and central nervous system pain processing systems, including mechanical pain sensitivity and temporal summation. QST testing will be done at baseline (no auditory stimulus of any kind) and then will be repeated within the same subject while listening to the auditory stimulus. Patients will be randomized to either the Music arm or the Placebo (nature sounds) arm. Half of the patients will listen to music, and half will listen to nature sounds during testing. Hypothesis 1a: We hypothesize that both listening conditions will reduce pain sensitivity (lead to higher pain thresholds and tolerance) as compared to the no-sound control. Hypothesis 1b: We hypothesize that the use of music listening during QST tasks will reduce pain sensitivity as compared to the use of only nature sounds. Aim 2: Identify whether the objective analgesic effects of music listening are associated with subjective measures of anxiety, pain catastrophizing, resilience, and measures of music experience and enjoyment. In order to accomplish this Aim, the degree of analgesic effect of auditory listening (as measured by the difference in QST measures between baseline and music listening) will be calculated and correlated to subjective measures of pain and other pain-related patient characteristics using patient-reported outcome (PRO) measures. Hypothesis 2: We hypothesize that greater analgesic effect of music listening will be associated with lower levels of anxiety, depression, and with higher levels of music experience and enjoyment.

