## II. Research Plan and Design

Overall Study Design. For Aims 1 and 2, we will enroll 40 patients with FM to undergo QST testing on two separate days: baseline (Testing As Usual, no sound) and auditory listening. Participants will be randomized to two auditory listening conditions: music listening and nature sound listening. The conditions will be counterbalanced across subjects such that some will have listening on their first testing day and no sound on the second, and the rest of the subjects will have no sounds on the first day and listening on the second. Participants will be seated in a quiet room and a heart monitor will be attached. The participant will wear headphones during all testing sessions (including the no-sound control). They will listen to 10 minutes of the specified auditory recording (or silence) prior to QST testing. The researcher will then conduct the QST while the participant continues to listen to the auditory recording. The study visit will last for approximately 1 hour. The researcher collecting QST data will be blinded to which recording the participant is hearing.

After screening, informed eConsent (paper consent forms will be available if requested), and enrollment into the study, all subjects will undergo an evaluation which includes a battery of questionnaires for patient phenotyping that will assess symptoms including pain, physical function, depression, anxiety, and catastrophizing symptoms. QST parameters will also be performed after questionnaire administration as described above.

Patient Population. Recruitment: Participants will be recruited from the KUMC [name], Comprehensive Spine and Pain Management Center's chronic pain clinics and surgical spine clinics. The Frontiers Registry and the Pioneers Community Research Recruitment Registry services through the Frontiers: The Heartland Institute for Clinical and Translational Research will also be used to foster the recruitment of participants from the community. We will also be using web-based recruitment pathways including Craig's List, social media, and the KUMC intranet. Patients will be paid for their time for all visits.

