# B. Study Type and Design:

This study is a pre-post interventional parallel randomized control trial pilot study. We will enroll 40 patients with FM to undergo QST testing on two separate days: baseline (Testing As Usual, no sound) and auditory listening. Participants will be randomized to two auditory listening conditions: music listening and nature sound listening. The conditions will be counterbalanced across subjects such that some will have listening on their first testing day and no sound on the second, and the rest of the subjects will have no sounds on the first day and listening on the second. Participants will be seated in a quiet room and a heart monitor will be attached. The participant will wear headphones during all testing sessions (including the no-sound control). They will listen to 10 minutes of the specified auditory recording (or silence) prior to QST testing. The researcher will then conduct the QST while the participant continues to listen to the auditory recording. The QST testing battery will last for approximately 1 hour. The researcher collecting QST data will be blinded to which recording the participant is hearing.

After screening, informed eConsent, and enrollment into the study, all subjects will undergo an evaluation which includes a battery of questionnaires for patient phenotyping that will assess symptoms including pain, physical function, depression, anxiety, and catastrophizing symptoms. QST parameters will also be performed after questionnaire administration as described above.

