## C. Sample size, statistical methods, and power calculation

Statistical Analysis: Data analysis will be performed by the KUMC Department of Biostatistics. The data analyst will also be blinded to whether data was during the nature sounds or music listening condition. Once all data have been collected and summary scores have been calculated, the database will be locked. Only then will the blind be broken for whether the QST scores were associated with music or nature sounds, and the final statistical test will be conducted.

Aim 1 Analyses: Pain thresholds and temporal summation scores will be treated as continuous measures and normality will be assessed prior to analysis. QST data will be analyzed using a paired t-test or appropriate nonparametric test to detect changes within-subject changes in QST measures between nature sounds or music listening.

Aim 2 Analyses: Magnitude of changes in QST measures between nature sounds and music listening will be calculated and correlated to the subjective measures of pain and music that are administered via patient-reported outcome questionnaires. All measures will be treated as continuous measures and normality will be assessed prior to analysis. These relationships will be analyzed using Pearson's correlation testing.

Sample size for Study Procedures in Aims 1 and 2: It is not possible to conduct adequate power analyses for the aims as this pilot study will be the first to measure QST changes with a music listening intervention in this patient population. Sample sizes for studies included in previous meta-analyses ranged from 25 to 175. We will use the data collected in this pilot study to estimate effect sizes for the next application for a larger trial.

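### Counterbalanced test days can balance drop-out for listening versus no sound, but not for music versus nature sounds (Hypothesis 1b), and the planned analyses discard one-session participants

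*Combined protocol and SAP*

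**What the plan says.** The safeguard is in section II, Mitigation of bias: "Our counterbalancing of testing days will help to ensure that attrition is not affecting one condition to a greater degree than another". Overall Study Design shows what is counterbalanced: "some will have listening on their first testing day and no sound on the second", with the reverse order for the others. The size of the split, and whether it is balanced within arm, are not given.

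The recording is allocated between participants. Specific Aims says: "Half of the patients will listen to music, and half will listen to nature sounds during testing". Hypothesis 1b is the contrast between those two groups: "We hypothesize that the use of music listening during QST tasks will reduce pain sensitivity as compared to the use of only nature sounds". Participants know what they hear: "Patients cannot be blinded as they will know whether they are hearing nothing, music, or nature sounds during testing".

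For Aim 1, section II.C says: "QST data will be analyzed using a paired t-test or appropriate nonparametric test to detect changes within-subject changes in QST measures". Aim 2 correlates changes in QST measures with the questionnaires. Enrolment is stated in section II.B: "We will enroll 40 patients with FM to undergo QST testing on two separate days". No expected drop-out rate, analysis set, missing-data rule or replacement rule is given.

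**The concern.** The attrition statement speaks of conditions in general, so a reader will take it to cover music versus nature sounds as well. Day order cannot equalise loss between two groups of different people.

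A participant who starts with no sound and does not return has not heard a recording. One who starts with listening has had a full session with the assigned recording during pain testing, and may decide about the second visit partly on that experience. Loss that depends on the recording can therefore arise in the listening-first half and differ between arms. A paired test or a change score needs both sessions, so these people leave the analysis and their valid first session goes with them.

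At stake are the Hypothesis 1b estimate and the effect sizes that section II.C intends to carry into the next trial. Both would come from completers only, while the protocol describes unequal attrition as already mitigated.

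**Working it through.** **The plan's own figure.** The sample of 40 has no significance level, power, effect size, SD or drop-out rate behind it, so there is nothing to reproduce. Everything below rests on assumptions: 10 participants per order within each arm of 20, change-score SD of 1, no true music-nature difference, and equal variances in the two sessions with correlation ρ.

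**1. Does counterbalancing help Hypothesis 1a?** Yes, under a condition. In a large-sample simulation where participants with the lowest first-session scores leave at the same rate (10% or 20%) after every first-day condition, complete pairs give a listening-versus-no-sound bias of about 0 when the order is counterbalanced. With one fixed order the bias is 0.05 to 0.18 SD in either direction (ρ from 0.85 to 0.5).

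**2. Does it help Hypothesis 1b?** Not when loss after listening differs by arm:

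| Loss after no sound / music / nature first | Completers, music | Completers, nature | Music minus nature bias (ρ 0.85 to 0.5) |
|---|---|---|---|
| 10% / 10% / 30% | 9 + 9 = 18 | 9 + 7 = 16 | -0.03 to -0.05 SD |
| 10% / 0% / 40% | 9 + 10 = 19 | 9 + 6 = 15 | -0.07 to -0.12 SD |

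The gap in completers is 10 × (nature-first loss − music-first loss). With everyone listening first, the same scenarios give -0.08 to -0.32 SD. With everyone on no sound first they give about 0, because first-day loss cannot then depend on the recording.

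**3. Loss on the observed first-session score, in one arm only.** Let a fraction q of that arm's listening-first half be lost, those with the lowest scores, and nobody else. The completers' inflation in that half is r·φ(z_q)/(1 − q), where r = √((1 − ρ)/2) is the correlation of the listening score with the change. That half makes up (1 − q)/(2 − q) of the arm's completers, so the arm-level bias is r·φ(z_q)/(2 − q).
- q = 0.10, ρ = 0.8: 0.316 × 0.1755/1.9 = 0.03 SD.
- q = 0.20, ρ = 0.7: 0.387 × 0.280/1.8 = 0.06 SD.
- q = 0.30, ρ = 0.6: 0.447 × 0.3477/1.7 = 0.09 SD.

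**4. Extreme case.** Exactly the 20% with the smallest change are lost (r = 1). The inflation in the half is 0.280/0.80 = 0.35 SD; over the arm it is 0.35 × 8/18 = 0.156 SD. These are large-sample values. With 10 people of whom the lowest two are lost, the expected values are 0.318 and 0.318 × 8/18 = 0.14 SD.

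**5. What a model that keeps one-session participants recovers.** A likelihood-based fit with condition, arm, their interaction and session day, at 20% loss, was compared with complete pairs for ρ from 0.5 to 0.8. When loss depends on the observed score, the bias falls from 0.05-0.08 SD to about 0. In the extreme case it falls only from about 0.156 to 0.12-0.14 SD.

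**6. Scale.** With 20 per arm, two-sided 5% and 80% power (assumed), the detectable difference in change is (1.960 + 0.842) × √(2/20) = 0.89 SD. With 18 versus 20 completers the standard error is √(1/18 + 1/20) = 0.32 SD.

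**The case against.** The strongest reply is that the sentence is about test days and claims only to help. Read as listening versus no sound it is partly right (step 1). That stands: a reader might infer that counterbalancing does nothing against attrition, and the documents do not support this.

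A reader might also infer that it is the only measure bearing on return. It is not. Study Limitations names a financial incentive to aid compliance, and the payment section credits the card once all procedures are done. Neither equalises loss between arms.

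Next, the extreme case strains belief. A listening-first participant has no change score yet when deciding whether to return, so selection exactly on that score is a bound rather than a forecast; in this design it concerns two people of 40. The visits are two laboratory sessions with payment, and nothing in the documents shows that people would leave because of the recording. All of this stands, and it limits the size of the point. Nor is the direction fixed: loss of poor responders from the nature arm would make music look worse.

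Finally, the paired test as written cannot estimate Hypothesis 1b at all, because nobody hears both recordings. That is a separate and prior defect. Replacing it with a between-arm comparison of change scores would still discard one-session participants, so the present point survives that repair.

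**Conclusion.** The stated attrition safeguard does not extend to Hypothesis 1b, and the planned analyses drop everyone with a single session. This follows from the design and needs no numerical assumption.

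The size does rest on assumptions. It is about 0.03-0.09 SD of change for 10-30% loss on the observed first-session score in the listening-first half of one arm (ρ 0.6-0.8), up to about 0.12 SD in the 40% versus 0% scenario, and 0.14-0.16 SD in the extreme case. All are well below the 0.32 SD standard error. A reader might infer that the Hypothesis 1b result will be biased, or biased towards music; with no drop-out rate in the documents, neither can be said. Importance is minor to moderate for a two-visit pilot, chiefly because the estimate feeds the next trial.

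**What to change.** - **Mitigation of bias:** say that counterbalancing balances test-day effects, and balances attrition for listening versus no sound when drop-out is similar in both orders, but does not protect music versus nature sounds.
- **Section II.C:** analyse every randomised participant with at least one QST session, in the assigned arm, with a likelihood-based mixed model containing condition (listening or no sound), arm, arm-by-condition interaction and session day. The interaction is the Hypothesis 1b estimate; without it the model does not address that hypothesis.
- **Sensitivity analysis:** keep the completers-only comparison of change scores between arms.
- **Reporting:** give non-return by arm and by first-session condition.

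The cost is wording in two places and a somewhat more complex model; no new patients, visits or measurements are needed. The downside is that the model removes bias only where non-return is explained by observed scores. The non-return table is therefore needed to judge how far that assumption can be trusted.

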## C. Rationale

The proposed study is significant as it will identify whether music listening has an analgesic effect during pain threshold and tolerance testing for patients with FM that supersedes any effect of auditory distraction. Results from the proposed study may provide objective evidence that music listening objectively improves analgesia and pain management and thus could be considered therapeutic during situations where acute pain is expected.

This study is innovative as it is the first to collect objective measures of within-subject change in pain

KUMC - HRPP- 03/12/2015

sensitivity in patients with FM using controlled, quantitative measures using a music listening intervention. Additionally, we will use specific pieces of classical music, clearly described in musical terms, for the listening intervention to control heterogeneity of response based on variability in musical parameters, such as tempo or instrumentation, which may impact the analgesic response. We will also use an active control condition of nature sounds to isolate the effect of music compared to another distracting stimulus. We have assembled a research team with expertise in chronic centralized pain syndromes and use of PROs and QST for clinical pain research ([name]) and music ([name]) to develop this research project, which will be utilizing rigorous methods currently used in [name] funded NIH work as well as having a strong foundation and rationale in music theory.

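### The no-sound control cannot isolate distraction: unblinded patients supply every QST score, so sound versus silence estimates the total effect of listening

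*Combined protocol and SAP*

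**What the plan says.** Each patient has two QST sessions on separate days, one in silence and one with the assigned sound, in counterbalanced order (II. Research Plan and Design). Hypothesis 1a, in the Specific Aims, is that "both listening conditions will reduce pain sensitivity (lead to higher pain thresholds and tolerance) as compared to the no-sound control". Hypothesis 1b compares music with nature sounds.

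Mitigation of bias draws the inference: with both controls, "we will be able to determine whether a) there is an analgesic effect of distraction in this population", and also whether music does more than another distracting sound. The same paragraph states: "Patients cannot be blinded as they will know whether they are hearing nothing, music, or nature sounds during testing".

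The QST section defines the scores. In the pressure test the patient rates each stimulus from 0 to 100, and the series stops at the patient's tolerance or at 10 kg/cm2. "Pressure pain threshold and tolerance will be determined from this procedure", and so is PAIN50. For the wind-up ratio, "patients will report the pain intensity of the pinprick sensation using a 0-100 NRS".

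The Abstract, Background and Rationale describe the expected result as objective; in the Rationale: "Results from the proposed study may provide objective evidence that music listening objectively improves analgesia and pain management". Aim 2 applies the same adjective to the listening-minus-baseline difference in QST.

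**The concern.** The safeguards are coded audio files, headphones in every session, a blinded tester, a blinded analyst and counterbalanced days. They deal with tester bias, analyst bias and order. None deals with what the patient expects, and the patient produces the score. A patient who tolerates more pressure with nature sounds than in silence may be distracted, may expect sound to help, or both.

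Expectation is foreseeable here. The consent form describes the purpose of the study, and the Background mentions expectations, though only as an effect of familiar music. Neither Mitigation of bias nor Study Limitations discusses patient expectation. The nearest items collected, familiarity and liking, are rated after each session and do not measure expected relief.

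At stake is how a positive Hypothesis 1a result is read, and what is carried forward. Section II.C says the data will supply effect sizes for a larger trial. An effect size from the silence contrast would be a total effect, not an effect of distraction.

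**Working it through.** The plan has no figure to reproduce. Section II.C declines a power analysis and gives no alpha, SD or effect size. The check is therefore mainly one of logic.

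**1. Who produces each score**

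| Score | Source | Tester blinded | Patient blinded |
|---|---|---|---|
| Threshold, tolerance, PAIN50 | Patient ratings and patient stopping point | Yes | No |
| Wind-up ratio | Ratio of mean patient ratings | Yes | No |

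**2. What the contrasts estimate**

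Let D be the effect of distraction, E the effect of expectation on response, and O any other non-specific effect of listening. With balanced order,

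mean(sound − silence) = D + E + O.

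Only the sum is identified. A result with D = 0.3 and E = O = 0 looks the same as one with E = 0.3 and D = O = 0. A larger sample narrows the interval around the sum but does not split it.

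For music versus nature sounds, with non-specific effects D and O alike in the two arms,

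(music − silence) − (nature − silence) = music-specific effect + (E_music − E_nature).

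If expected relief is the same for both sounds, the last term is zero. If not, the difference in expectation remains. This contrast is randomised and both arms hear a sound, so it is better protected, though not fully.

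**3. Illustration of size**

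Assumptions, none from the documents: a two-sided 5% paired t-test of sound versus silence, D = O = 0, and an expectation shift b in SDs of the within-patient difference. Inputs from the plan: 40 patients in all, half in each arm, so 20 per arm. Noncentrality is b × √n, with √40 = 6.32 and √20 = 4.47.

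| b | b√40 | P(significant), 40 pairs | b√20 | P(significant), 20 pairs |
|---|---|---|---|---|
| 0 | 0 | 5% | 0 | 5% |
| 0.2 | 1.26 | 23% | 0.89 | 14% |
| 0.3 | 1.90 | 46% | 1.34 | 25% |
| 0.4 | 2.53 | 69% | 1.79 | 40% |
| 0.5 | 3.16 | 87% | 2.24 | 56% |

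A true distraction effect of the same size gives the same probabilities, which restates step 2.

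**4. The wind-up ratio behaves differently**

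Take illustrative mean ratings of 40 for the train and 20 for the single stimulus: 40/20 = 2.0. If listening lowers both by a fifth, 32/16 = 2.0 and the shift cancels. If it lowers both by 5 points, 35/15 = 2.33 and the ratio rises. A report shift therefore need not act on all QST scores alike, or in the same direction.

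**The case against.** Patients cannot be blinded to an audible intervention, and the plan says so openly. It adds an active control for non-musical effects, of which distraction is given as an example rather than the only one. It already rests the claim that music goes beyond distraction on that control. It is a 40-patient pilot. All of this stands. It means the trial can proceed as designed. It does not rescue the statement that the silence contrast will determine an effect of distraction.

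Several stronger readings are tempting, and the documents do not support them.

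- *A reader might infer that the plan promises objective proof of analgesia from distraction.* It does not. The Abstract, Background and Rationale say the results may provide such evidence, and there the word attaches to music, with the stated aim of an effect beyond distraction. The distraction sentence does not use the word. In Aim 2 it sets QST apart from questionnaires. It can fairly mean a calibrated stimulus: computer-delivered pressure or a fixed 256 mN pinprick. What needs saying is that the response is still the patient's.
- *A reader might take the percentages as this trial's false-positive rate.* They are a generic power curve at assumed shifts and an assumed 5% level. Section II.C names no sound-versus-silence test.
- *A reader might conclude that an expectation covariate would solve the problem.* Expected relief for the assigned sound would use the music item in one arm and the nature item in the other, so it depends on arm by construction. Adjusting for it could remove part of the randomised music effect. Asking about relief may also prime patients, and equal priming in both arms does not cancel in a within-patient comparison with silence.
- *A reader might look to the ECG.* Its named comparisons are passive versus active listening and nature sounds versus music, not sound versus silence. Heart rate may itself respond to expectation or emotion.

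**Conclusion.** The point holds for the silence contrast. Mitigation of bias states an inference that the design cannot deliver: sound versus known silence, scored by the patient, estimates distraction, expectation and other non-specific effects combined, at any sample size. This rests only on the plan's own account of blinding and scoring. It does not depend on any assumed size of expectation.

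The documents do not allow that size to be estimated. The 0.2 to 0.5 SD shifts are illustrative only. They show that a modest expectation effect could by itself often give a significant silence contrast, not that it will.

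Hypothesis 1b is not invalidated. It remains the right basis for claims about music beyond non-specific effects, with the reservation that expected relief may differ between music and nature sounds.

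**What to change.** 1. **Mitigation of bias.** Replace the claim about determining an effect of distraction. Suggested text: *The comparison of listening with no sound estimates the total effect of listening, in which distraction, expectation and other non-specific effects are combined. Claims that music acts beyond such effects rest on the randomised comparison of music with nature sounds, recognising that expected relief may differ between the two.*
2. **Study Limitations.** List patient expectation as a limitation of Hypothesis 1a.
3. **Abstract, Specific Aims, Background and Rationale.** Where the text says *objective*, state that QST applies a standardised stimulus and records a participant-reported response.
4. **Optional.** A three-item form asking expected relief from music, nature sounds and silence, completed before the assigned sound is known. Report it descriptively, or enter the same two differences (music minus silence, nature minus silence) for every patient in both arms as exploratory baseline covariates. State that the form may prime the silence contrast and cannot remove the confounding.

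Items 1 to 3 cost only wording, and a more modest claim for Hypothesis 1a. Item 4 costs one short form in REDCap and some risk of priming. Leaving it out is defensible.
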